**Table 1. Device Sizing Matrices**

[figure not shown]
Aortic Body		Iliac Limb / Extension	
Stent Graft Diameter, mm	Aortic ID, mm*	Stent Graft Diameter, mm	Iliac ID, mm
20	16-17	10	8-9
23	18-20	12	10-11
26	21-23	14	12-13
29	24-26	16	14-15
34	27-30	18	16-17
		22	18-20
		28	21-25

\* At the intended proximal sealing ring location (7 mm below the inferior renal artery). Ensure adequate oversizing of the proximal stent at its anchoring location.

[figure not shown]
The Fill Kit options are shown in Figure 7 and Figure 8. Figure 7 is the Fill Polymer Kit with 20 minute detach time and Figure 8 is the CustomSeal Kit with 14 minute detach time. The

fill polymer is comprised of three components that are mixed prior to injection. Upon mixing and injection into the graft, the components form a radiopaque polymer that fills the sealing rings in the wall of the aortic body graft and the ribs in the aortic body graft legs. The fill polymer radiopacity dissipates over time and may not be visible on fluoroscopy, X-ray or CT beyond 1-2 months post-implant.

[figure not shown]
Prior to use, the two valves on the fill kit are opened and the fill polymer is mixed by alternately depressing the two syringe plungers for a minimum of 20 full strokes. Thereafter, the fill syringe is disconnected from the connection tube, slipped out of the syringe support and connected to the fill polymer injection port on the aortic body delivery system. The syringe plunger is then inserted into the Autoinjector (Figure 9), and the Autoinjector is given a quarter-turn to lock it in place. The Autoinjector applies controlled force to the syringe plunger to inject the fill polymer into the graft.

**Figure 7.** Fill Polymer Kit with 20 minute detach time

**Figure 8.** CustomSeal Kit with 14 minute detach time

**Figure 9.** Autoinjector or Autoinjector 2

**Table 2. Balloon Expandable Stent sizes**

Stent Graft Length, mm	Catheter Working Length, cm	Delivery System Outer Profile, F	Integral Sheath Inner Diameter, F
30	60	12	10
40			

## 5.0 STUDY DESIGN

The goal of the study is to evaluate the Ovation Alto Abdominal Stent Graft System in subjects with abdominal aortic aneurysm (AAA). This prospective case series will consecutively enroll patients with AAA who will be treated with the Ovation Alto Abdominal Stent Graft System. The primary study objective of the study is to evaluate treatment success at 12 months in patients treated with Ovation Alto. Secondary objectives of this study will include safety and effectiveness assessments of the Ovation Alto device through 12-month follow-up.

Subjects will be screened prior to study entry to determine if they meet the eligibility criteria. Subjects, or, when appropriate, the subject's legal representative, will give informed consent following an explanation by the investigator of the risks and benefits of treatment with the Ovation Alto Abdominal Stent Graft System. A screening log will be maintained of all subjects evaluated for inclusion in this study to document the reasons for non-eligibility. Each study center may enroll and treat up to 20% of the total study population.

### 5.1 Eligibility Criteria

The inclusion/exclusion criteria in this study are identical to the Ovation Abdominal Stent Graft System IDE G090239, with the exception of Inclusion Criteria 7, 8, and 10 below, which are specific to the Ovation Alto Abdominal Stent Graft System device sizing.

#### 5.1.1 Inclusion Criteria

Patients must meet all of the following inclusion criteria to be eligible for enrollment into this study:

1. Patient is  $\geq 18$  years of age.
2. Patients who are male or non-pregnant female (females of child bearing potential must have a negative pregnancy test prior to enrollment into the study).
3. Patient has signed an Ethics Committee/Institutional Review Board (IRB) approved Informed Consent Form.
4. Patient is considered by the treating physician to be a candidate for elective open surgical repair of the AAA (i.e., category I, II, or III per American Society of Anesthesiology (ASA) classification; refer to **Appendix III: ASA Classification System**). ASA category IV patients may be enrolled provided their life expectancy is greater than 1 year.
5. Patient has an infrarenal abdominal aortic aneurysm that meets *at least* one of the following:
  - (a) Abdominal aortic aneurysm  $\geq 5.0$  cm in diameter,

- (b) Aneurysm that has increased in size by 0.5 cm in last 6 months\*,
- (c) Maximum diameter of aneurysm exceeds 1.5 times the transverse dimension of an adjacent normal aortic segment\*.

\*As part of the ELEVATE IDE Study, abdominal aortic aneurysms that are less than 5 cm in diameter may be treated, if at least one of the following anatomical criteria is met:

- Aneurysm has increased in size by at least 0.5 cm in the last 6 months
- Aneurysm is no less than 4 cm in diameter and exceeds 1.5 times the transverse dimension of the an adjacent normal aortic segment, as demonstrated on the screening CTA, performed within 6 months of anticipated treatment.

6. Patient has patent iliac or femoral arteries that allow endovascular access with the Ovation Alto Abdominal Stent Graft System.
7. Patient has a proximal aortic landing zone with an inner wall diameter of no less than 16 mm and no greater than 30 mm at 7 mm below the inferior renal artery.
8. Patient has an adequate distal iliac landing zone with an inner wall diameter of no less than 8 mm and no greater than 25 mm.
9. Patient has an adequate distal iliac landing zone with a length of at least 10 mm. The resultant repair should preserve patency in at least one hypogastric artery.
10. Patient meets the following anatomic criteria: the distance from the most distal renal artery to most superior internal iliac artery measurement is at least 125 mm.
11. Patient has juxtarenal aortic neck angulation  $\leq 60^\circ$  if proximal neck is  $\geq 7$  mm and  $\leq 45$  degrees if proximal neck is  $< 7$  mm.
12. Patient must be able and willing to comply with all required follow-up exams.

### ***5.1.2 Exclusion Criteria***

Patients that meet ANY of the following are **not** eligible for enrollment into the study:

1. Patient has a dissecting aneurysm.
2. Patient has an acutely ruptured aneurysm.
3. Patient has an acute vascular injury.
4. Patient has need for emergent surgery.
5. Patient has a known thoracic aortic aneurysm or dissection.
6. Patient has a mycotic aneurysm or has an active systemic infection.
7. Patient has unstable angina (defined as angina with a progressive increase in symptoms, new onset at rest or nocturnal angina, or onset of prolonged angina)
8. Patient has had a myocardial infarction (MI) and/or stroke (CVA) within the past 6 months.
9. Patient has a major surgical or interventional procedure planned 30 days prior and 30 days post procedure of the AAA repair.

- 
10. Patient has history of connective tissue disease (e.g., Marfan's or Ehler's–Danlos syndrome).
  11. Patient has history of bleeding disorders or refuses blood transfusions.
  12. Patient has dialysis dependent renal failure or baseline serum creatinine level >2.0 mg/dl.
  13. Patient has a known hypersensitivity or contraindication to anticoagulation or contrast media that is not amenable to pre-treatment.
  14. Patient has a known allergy or intolerance to polytetrafluoroethylene (PTFE), polyethylene glycol (PEG) -based polymers, fluorinated ethylene-propylene (FEP) or nitinol.
  15. Patient has a body habitus that would inhibit X–ray visualization of the aorta.
  16. Patient has a limited life expectancy of less than 1 year.
  17. Patient is currently participating in an investigational device or drug clinical trial.
  18. Patient has other medical, social or psychological conditions that, in the opinion of the investigator, preclude them from receiving the pre-treatment, required treatment, and post-treatment procedures and evaluations.

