## 4.0 DEVICE DESCRIPTION

The Ovation Alto Abdominal Stent Graft System is an endovascular device delivered via a low-profile catheter to treat abdominal aortic aneurysms (AAAs). The stent graft is designed to reline the diseased vasculature, providing an endovascular blood conduit for isolating the aneurysm from the high-pressure flow of blood, thereby reducing the risk of rupture. The stent graft is a modular configuration comprised of an aortic body section, iliac limbs, the balloon expandable stent/delivery system as required, as well as iliac extensions as required (Figure 1).

The Ovation Alto Abdominal Stent Graft System includes:

- An Aortic Body Stent Graft and delivery catheter
- Ovation iX Iliac Limb Stent Grafts and delivery catheters\*
- Ovation iX Iliac Extension Stent Grafts and delivery catheters, as required\*
- Balloon Expandable Stent and delivery catheters, as required
- A Fill Kit\*
- An Autoinjector

[figure not shown]
\*Note: These components are currently approved by FDA via PMA P120006.

**Figure 1.** Schematic of Deployed Ovation Alto Abdominal Stent Graft System

The aortic body is comprised of a proximal stent for suprarenal fixation and a low-permeability polytetrafluoroethylene (PTFE) graft. The stent is designed with integral anchors to enable fixation to the aortic wall. For delivery, the stent is in a compressed state within the catheter. When released from the compressed state, the stent expands to engage the vessel wall. The nitinol stent is radiopaque, and radiopaque markers are located adjacent to the graft proximal edge. These radiopaque markers aid placement of the device in its intended location relative to the renal arteries. To seal the proximal end of the graft and to provide support for the aortic body legs into which the iliac limbs are deployed, the graft body contains a network of inflatable rings that are filled with a liquid polymer that solidifies during the deployment procedure. The graft has a fill port that connects the fill network of the graft to the delivery catheter. Figure 2 provides an image of the device with its sealing ring in the aorta.

[figure not shown]

**Figure 2.** Ovation Alto Aortic Body Stent Graft in aorta

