The iliac limbs and extensions are comprised of a nitinol stent encapsulated in low-permeability PTFE. The iliac limbs are deployed into the leg sections of the aortic body. Radiopaque markers enable the physician to visualize the appropriate iliac limb - aortic body overlap or iliac extension – iliac limb overlap during a catheter-based deployment. Stent radial force provides both fixation and sealing of the interface between the aortic body and each iliac limb, between the iliac limb and iliac extension, and between the iliac limb/extension and its landing zone in the iliac artery.

The BES implant is a balloon expandable, closed cell design, laser cut stent made from seamless 316LVM stainless steel tubing. The implant is supplied in two nominal lengths, 30mm and 40mm, and is preloaded into a delivery catheter. The implant is designed to expand to a maximum diameter of 30mm. The stainless steel stent is inherently radiopaque which visually aids the placement of the stent graft accessory across the sealing rings of the primary aortic stent graft body as illustrated in Figure 3 below.

**Figure 3.** Balloon Expandable Stent in Ovation Alto Stent Graft

To facilitate device introduction into the access vessel, the aortic body, the iliac limbs, the iliac extensions, and the balloon expandable stent are preloaded into delivery catheters, as illustrated in Figures 4-6. The delivery catheters each have a lumen for use with a guidewire to facilitate access and deployment and the outer sheaths are hydrophilically coated. The inner catheter of each delivery system can be withdrawn through the outer sheath, with the outer sheath remaining in the vasculature to facilitate the introduction of ancillary devices.

The aortic body is deployed via the aortic body delivery catheter, which has a connection to the distal legs of the aortic body. During aortic body stent graft deployment, the device is first positioned and the sheath is retracted. The proximal stent is deployed using stent release knobs on the handle, with an integral balloon used to facilitate graft opening. The fill polymer is then delivered through the fill connector port using the Autoinjector.

[figure not shown]

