The contralateral and ipsilateral iliac limbs are each deployed via iliac limb delivery catheters. After deployment of the aortic body, a guidewire is placed from the contralateral access site into the contralateral distal leg of the aortic body; the integrated crossover lumen on the aortic body delivery system can be utilized to facilitate the process. The contralateral iliac limb is advanced into position and deployed into the aortic body leg by retracting the catheter sheath with the catheter in the appropriate position. The contralateral limb delivery catheter is then used as an integral sheath (as described above) or withdrawn from the vasculature.

After the fill polymer cures within the sealing rings, the integral balloon of the aortic body delivery catheter can be used to improve seal ring apposition. The catheter is detached from the fill port of the graft and is used as an integral sheath (as described above) or withdrawn from the vasculature.

[figure not shown]
The ipsilateral iliac limb delivery catheter is advanced over the ipsilateral guidewire and deployed using the method described above for the contralateral limb. The ipsilateral limb delivery catheter is then used as an integral sheath (as described above) or withdrawn from the vasculature.

If an iliac extension is required, the delivery system is advanced over the guidewire and deployed using the method described above for contralateral and ipsilateral iliac limbs.

[figure not shown]
If a balloon expandable stent is required (after removal of the aortic body delivery system), the stent is first positioned across the sealing ring and secondary ring of the previously deployed aortic body stent graft and the sheath is retracted. After sheath retraction, the stent is expanded by inflating the balloon while aligning the proximal crowns of the stent with the aortic body stent graft radiopaque markers. The balloon is then deflated and the delivery catheter is withdrawn from the vasculature.

**Figure 4.** Schematic of Ovation Alto Abdominal Stent Graft System Aortic Body Delivery Catheter

**Figure 5.** Schematic of Ovation iX Iliac Limb/ Iliac Extension Delivery Catheter

**Figure 6.** Schematic of Balloon Expandable Stent Delivery Catheter

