#### **5.5.1.2 Pre-procedure Evaluation**

The following assessments will be performed no more than one month prior to the implant/surgical procedure:

- Patient demographics
- Medical/surgical history
- Physical exam
- Ankle-Brachial Index (ABI)
- Laboratory testing, which includes renal assessment and serum pregnancy for female patients of childbearing potential.

If the patient is eligible to be enrolled into the study, the results of these screening assessments are recorded on the **Baseline eCRF**. If a patient is not enrolled into the study, the baseline screening worksheets will be retained, together with the patient's signed/dated consent(s).

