## 9.0 RISK ANALYSIS

Treatment of an AAA with both endovascular and open surgical repair poses significant inherent risks to the subject. The mortality risk of open surgical repair of an AAA is greater for those subjects with significant surgical risk factors, such as age and comorbidities (e.g., cardiac, renal and pulmonary).

Endovascular treatment of a AAA has been shown to be an effective, less invasive procedure that may result in reduced early mortality and factors related to morbidities, reduced time for anesthesia, need for blood products, shorter hospital stays and recovery time, as well as improved quality of life in the early postoperative period.

Risks to subjects are minimized initially by including those patients that are considered to be suitable candidates for open surgical repair and by selecting qualified investigators/institutions with endovascular experience to participate in the study. In order for patients to participate in this study, they must agree to adhere to a strict follow-up schedule to continuously monitor their long term safety.

The risks associated with the use of this study device are not currently known. Although the adverse events associated with the use of the Ovation Alto Abdominal Stent Graft System may be less than for standard open surgical repair, inherent risks exist, as with many medical procedures. However, risks that have been associated with repair of AAAs with this type of device in clinical trials or that are currently marketed include, but may not be limited to:

- Acute and chronic renal failure, renal microembolism, renal insufficiency, renal artery occlusion, contrast toxicity;
- Allergic reaction and/or anaphylactoid response to x-ray contrast dye, anti-platelet therapy, device materials;
- Anesthetic complications and subsequent attendant problems (aspiration);
- Aneurysm enlargement or rupture;
- Blood or bleeding events such as anemia, gastrointestinal bleeding, retroperitoneal bleeding;
- Bowel events such as bowel ischemia, infarction, bowel necrosis, colon ischemia, paralytic or adynamic ileuses, obstruction, fistulas;
- Cardiac events and subsequent attendant problems such as congestive heart failure, volume overload, arrhythmias, myocardial infarction, chest discomfort or angina, elevations in creatinine phosphokinase (CPK), hypotension, hypertension;

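### Exclusion 14 names the device materials that bar a patient but leaves out stainless steel, the material of a stent in the study system

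*Combined protocol and SAP*

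**What the plan says.** Exclusion 14 in protocol Section 5.1.2 applies to a patient with a "known allergy or intolerance to polytetrafluoroethylene (PTFE), polyethylene glycol (PEG) -based polymers, fluorinated ethylene-propylene (FEP) or nitinol". It has no closing phrase that extends it to other materials in the device.

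The component list in Section 4.0 includes "Balloon Expandable Stent and delivery catheters, as required". The same section describes the component: "The BES implant is a balloon expandable, closed cell design, laser cut stent made from seamless 316LVM stainless steel tubing". When it is needed, the stent is expanded across the sealing ring and secondary ring of the aortic body, after the aortic body delivery system has been removed.

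On the origin of the criteria, Section 5.1 states: "The inclusion/exclusion criteria in this study are identical to the Ovation Abdominal Stent Graft System IDE G090239". The only exceptions it gives are inclusion criteria 7, 8 and 10, so exclusion 14 is presented as carried over. Section 9.0 lists among the risks "Allergic reaction and/or anaphylactoid response to x-ray contrast dye, anti-platelet therapy, device materials".

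**The concern.** A criterion that lists device materials one by one invites the reader to treat the list as complete. An investigator working through exclusion 14 would ask about four materials and could reasonably conclude that material allergy had been covered. Steel would not come up, and no other inclusion or exclusion criterion names it.

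What is at stake is the safety of an individual patient; the trial's inference is not touched. Someone with a known steel intolerance could be enrolled, and the question of placing a steel implant might then arise during the procedure, with the aortic body already deployed. An operator who then withheld the stent and turned to an unplanned third-party implant to treat or exclude the aneurysm would meet the Protocol Summary's definition of an unanticipated corrective intervention. Screening beforehand avoids that choice.

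**Working it through.** **Materials side by side**

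| Item | Where the document puts it | Covered by exclusion 14? |
|---|---|---|
| PTFE | Section 4.0: graft of the aortic body; covering of the iliac limbs and extensions | Yes |
| Nitinol | Section 4.0: proximal stent; stents of the iliac limbs and extensions | Yes |
| PEG-based polymers, FEP | Named in exclusion 14; not named in Section 4.0 | Yes |
| 316LVM stainless steel | Section 4.0: balloon expandable stent | No |

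Section 4.0 names two implant metals. Exclusion 14 covers one of them.

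**What else could catch the patient**

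- Exclusion 18 lets the investigator exclude for other medical conditions that preclude the required treatment. It mentions neither allergy nor steel, so it works only if the intolerance is already known to the investigator.
- Section 5.5.1.2 requires a medical and surgical history before the procedure. This may bring the intolerance out, but nothing in the text directs a question to steel.
- Section 5.5.1 says placement follows the IFU. The IFU is not part of the documents and may contain a warning.

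**Rough size**

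The documents give neither rate, so both ranges below are assumptions.

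- N = 75, the maximum enrolment (Section 8.5).
- p = prevalence of known steel intolerance, assumed 0.001 to 0.01.
- u = proportion of subjects who receive the stent, assumed 0.05 to 0.50.

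Expected subjects with the intolerance = N × p:
- low: 75 × 0.001 = 0.075
- high: 75 × 0.01 = 0.75

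Expected subjects with the intolerance who also receive the stent = N × p × u, taking the two as independent:
- low: 75 × 0.001 × 0.05 = 0.00375
- high: 75 × 0.01 × 0.50 = 0.375

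Both quantities stay below one subject across the whole range.

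**Effect on the statistical design**

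None. With n = 60, a performance goal of 80%, an assumed success rate of 92.8% and a one-sided exact 5% test, success requires at least 54 of 60. The exact type I error is 0.0308 and the power 0.8611, which agrees with the 86.1% stated in Section 8.5. The wording of exclusion 14 enters none of these figures.

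**The case against.** The strongest counter-argument is that the list may be intended. Nitinol and PTFE are in the aortic body and iliac limbs, which form the main implant. The balloon expandable stent is optional. An absolute bar for materials in the main implant, with an optional part left to the operator, is a defensible design. Adding steel could exclude a patient over a component that would never have been used.

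The revision history can be read either way. Revision B added the description of this stent and clarified inclusion 5 and exclusion 9, and it logs no change to exclusion 14. That fits a deliberate decision as well as an oversight. Whether the earlier IDE's system included this stent cannot be seen from these documents.

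There are also other safeguards: exclusion 18, the baseline history, training that covers subject selection (Section 12.0), a sponsor representative at each implant (Section 10.9), and possibly the IFU. Because exclusion 14 covers only known allergies, adding steel would still depend on the history. Finally, the assumed rates have no source, and they yield less than one affected subject.

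Most of this stands as a limit on importance. The omission cannot be called an error of transcription, and no section claims that exclusion 14 covers every device material. It does not close the gap. A patient with a known steel intolerance still passes the material criterion, the safeguards work only if someone raises the matter, and the protocol gives no reason for treating steel differently.

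**Conclusion.** The point holds as a minor improvement to eligibility wording. The text alone establishes that the material list is incomplete against Section 4.0. The practical size is very small: under the assumed rates, fewer than 0.4 of up to 75 subjects would have a known steel intolerance and receive the stent. Those counts only indicate scale and are not evidence of harm. Whether the omission was intended cannot be determined, and the IFU, which was not available, may already give some protection. The primary endpoint, its analysis, the sample size and the power are unchanged.

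**What to change.** Add stainless steel (316LVM) to exclusion 14 as a fifth material, after nitinol. Add the same item to the baseline screening worksheet if it is not already there. The worksheet itself is not supplied; Section 5.5.1.2 says only that, for patients not enrolled, "the baseline screening worksheets will be retained". If the sponsor left steel out on purpose because the stent is optional, one sentence in Section 5.1 giving that reason, with an instruction not to use the stent in a patient with known intolerance, would also settle the point.

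The cost is a one-line amendment and a worksheet update. The downside is possibly one fewer eligible patient, who might never have needed the stent. Exclusion comes before enrolment, so the next eligible patient can take the place and the target of 60 evaluable subjects is not affected.
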